8.4 Exploratory analysis

Tissue, blood and urine will be collected for biomarker analysis as part of the study. Requirements for biomarkers analysis are described in PCR-MIB Biomarker Laboratory Manual.

Resected tumour specimens will be available from the patients enrolled on the trial. These pre-treatment specimens will be comprehensively profiled for the abundance and composition of tumour infiltrating lymphocytes (CD4, CD8, CD3, CD20 and FoxP3 positive cells) by immunohistochemistry using the state-of-the-art Vectra Automated Imaging system recently acquired by the ONJCRI which enables multiplexed immunohistochemical analysis. Descriptive statistics will quantify individual immune parameters and correlation with response.

Blood samples collected prior to treatment, at the end of chemoradiotherapy, and after 24 weeks will be collected from the patients on the trial. PBMCs will be isolated using Ficoll, and changes in specific immune subpopulations (number/ratio) determined by multi-parameter FACS. Changes in the immune regulatory molecules OX-40/LAG3/PD1/ICOS on T cell subsets will be assessed by flow cytometry. Descriptive statistics will quantify individual immune parameters and correlation with response.

Changes in gene expression in CD3+ cells pre and post-treatment will be determined by RNAseq analysis to assess for gene expression changes associated with immune activation [9]. Descriptive statistics will quantify individual immune parameters and correlation with response.

Finally, to independently monitor B cell responses, pre- and post-treatment serum samples from the 30 trial patients will be analysed using CT100 microarrays for changes in titres of 100 cancer-testis auto-antibodies [10]. Descriptive statistics will quantify individual immune parameters and correlation with response.

Other immune endpoints potentially measurable using the biomarker resources from the trial include but are not limited to circulating DNA, antibody titres, peripheral blood markers of immune change and urine detectable immunological markers.

8.5 Timing of Analyses

A total of three analyses will be performed.

1. The interim analysis for the primary objective (feasibility) will take place after the 10th patient has reached the 31 week assessment time point.
2. Provided that the interim analysis does not result in the trial being closed prematurely due to unacceptable toxicity, the final analysis for the primary objective will take place after the last patient has reached the 31 week assessment time point.
3. Provided that the interim analysis does not result in the trial being closed prematurely due to unacceptable toxicity, the analysis for the secondary efficacy objectives, as well as the analysis of any exploratory objectives, will take place after the last patient has reached 3 years past registration.

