Additionally, any serious adverse event, considered by an investigator who is a qualified physician to be related to study treatment that is brought to the attention of the investigator at any time outside of the time period specified in the previous paragraph also must be reported immediately to the BaCT Trial Centre and to Merck.

SAE reports and any other relevant safety information are to be forwarded within 24 hours to:

BaCT Safety: [contact]

Merck Global Safety [contact]

ANZUP Safety: [contact]

All participants with serious adverse events must be followed up for outcome.

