7.2.9 Sponsor Responsibility for Reporting Adverse Events and Serious Adverse Events

The Sponsor is responsible for:

- Implementing and maintaining a suitable recording system to record information from all SAEs received from Trial Sites.
- Ensuring that the coordinating principal investigator (CPI) or delegate is notified of each SAE to enable the SAE to be assessed by the CPI and any other appropriate reviewers for nature (expected/unexpected), causality and whether the TGA needs to be notified of the SAE.
- Under the direction of the CPI or delegate, notifying the TGA (Australia) in accordance with the regulatory authority's detailed guidance of any SUSARs that are fatal or life threatening as soon as possible but no later than 7 days after the site gained first knowledge of the event. Incomplete reports must be completed and forwarded as soon as possible within 8 additional calendar days. All other serious, unexpected ADRs should be reported to the TGA within 15 days after the site gained first knowledge of the event.
- Considering information provided by (non-serious) adverse event data.
- Informing each trial site of new information arising from serious and non-serious adverse events and adverse drug reactions that may affect the conduct of the Trial, or the rights, interests, safety or wellbeing of Trial Participants.
- Under the direction of the CPI or delegate, notifying the TGA of any significant issue that has arisen from analysis of overseas reports or action that has been taken by another country's regulatory authority within 72 hours of first knowledge.
- Reporting Serious ADRs to the responsible HREC according to local requirements

The Investigator at each Trial Site is responsible for reporting Serious ADRs to the responsible Research Governance Office (RGO) according to local requirements.

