8.2 Sample Size Calculation

In order to justify continuing to explore pembrolizumab in combination with chemoradiation in a larger study, we must establish that the true underlying risk of unacceptable toxicities (UT's) in the population is acceptably low. To this end we need to decide upon values for a number of important parameters. Firstly, we need to decide upon a decision threshold for the maximum number of UT's allowable in the study sample before we conclude that the regimen is unsafe. In the event that the regimen is concluded to be unsafe, it should either be modified upon recommendation of the TMC before being considered further, or abandoned.

Additionally, we need to define two limits on the true underlying UT rate. The first is a “definitely considered safe” limit, defined such that if the true underlying UT rate is at this limit (or below) then we want to be confident that our decision threshold on the sample will yield a high probability that we will continue into a larger study focused on efficacy. The second is a “definitely considered unsafe” limit, defined such that if the true underlying UT rate is at this limit (or above) then we want to be very confident that our decision threshold on the sample will yield a high probability that we will discontinue – i.e. that we will reject the regimen as it currently stands for further consideration, and defer to the TMC for direction on whether and how to modify it.

To further mitigate risk, we would like accrual to proceed in two stages, with an interim analysis after the first stage at which stopping will be considered if the early evidence of a too high rate of UT's is convincing.

Under the proposed design, we desire to constrain the probability of discontinuation if the true underlying UT rate is at the definitely considered safe limit to a maximum of 20%, and at the same time limit the risk of continuing if the true underlying UT rate is at the definitely considered unsafe limit to 10%. We would like to consider the “definitely considered safe” rate of UT's to be 30%, and the “definitely considered unsafe” rate of UT's to be 50%.

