These goals can be achieved with a sample size of 30 patients. Consider a Simon's two stage design whereby accrual will be halted if we see greater than 5 UT's amongst the first 10 patients and greater than 11 amongst the first 30 patients. Given these stopping thresholds, if the true underlying UT rate is 0.3 then the cumulative probability of concluding unsafe after stage 2 of accrual will be 17% and if the true underlying rate of UT is 0.5 then the cumulative probability of concluding unsafe after stage 2 of accrual will be 90%. The relationship between the true underlying UT rate and the probability of concluding unsafe is shown in Figure 2.

[figure not shown]

Figure 2: Probability of concluding unsafe as a function of true underlying UT rate

As a secondary objective, we desire to test for an initial signal of efficacy by estimating the proportion of patients achieving a best response of complete response (CR). (See sections 3.2 and 7.1.2.6.2 for the definition of best response.) Similar to the procedure for placing thresholds on the number of UT's we define a threshold for the minimum number of CR's that must be seen in the sample in order to consider the regimen worthy of further investigation on the basis of efficacy. We also define a "maximum uninteresting" true underlying CR rate – the true underlying CR rate at or below which we would not consider the regimen clinically worthy of implementation, and a "minimum interesting" true underlying CR rate – the true underlying CR rate at or above which we would consider the regimen clinically worthy of implementation. We define the maximum uninteresting and the minimum uninteresting rates as being 0.5 and 0.7 respectively. If we place the decision threshold at 18 CR's out of 30, then the probability of judging the regimen worthy of further investigation for efficacy if the true underlying CR rate is 0.5 is 10%, and the probability of judging the regimen worthy of further investigation for efficacy if the true underlying CR rate is 0.7 is 84%. This is illustrated in Figure 3.

[figure not shown]

Figure 3: Probability of further investigation as a function of true underlying CR rate.

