9.0 SAFETY PARAMETERS/REVIEW AND MODIFICATIONS TO TRIAL

Given the experimental nature of the addition of pembrolizumab to concurrent chemoradiation, the following safety measures will exist

- 1) The trial operations executive (TOE) and the trial management committee (TMC) will review safety issues related to the trial through regular teleconferences held throughout the trial.
- 2) An additional safety review by the TMC will take place 12 weeks after completion of treatment for the 10th patient whereby accrual will be halted if we see greater than 5 UT's amongst the first 10 patients recruited using the Simon's two stage design described above in 8.2. Accrual can continue until the results of the interim analysis are available to the TMC.
- 3) Modifications to trial
 - a. Based on safety discussion the TMC may recommend to either
 - i. Omit concurrent pembrolizumab with chemoradiotherapy, and give pembrolizumab 200mg IV q3 weekly at week 7, 10, 13, 16 and 19 alone
 - ii. Modify the chemotherapy arm to allow either carboplatin, or 5FU/MMC [8]
 - iii. Suspend the study

iv. Any other modification suggested to reduce toxicity made by the TMC

The enrolment to the trial will be monitored by the TMC and if enrolment is reduced due to concerns regarding design of the trial, the TMC will suggest modifications that may include modification of the chemotherapy arm to allow concurrent carboplatin or 5FU/MMC.

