11.0 STUDY COMMITTEES

11.1 Trial Management Committee

This study is conducted by the Australian and New Zealand Urogenital and Prostate Cancer Trials Group (ANZUP) in collaboration with the Centre for Biostatistics and Clinical Trials (BaCT) who will coordinate this study

Study coordination, data acquisition and management and statistical analysis will be performed by the Centre for Biostatistics and Clinical Trials at Peter Mac.

The Trial Management Committee (TMC) will oversee study planning, monitoring, progress, review of information from related research, and implementation of recommendations from other study committees and external bodies (e.g. ethics committees).

The TMC will consider whether to continue the study as planned, modify, or stop it, based on reports provided by the BaCT or other information.

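### Section 8.2 words the limit of more than 11 unacceptable toxicities in 30 as halting accrual, but as scheduled it can act only as the final verdict; a running count to the 12th event would be a cheap improvement.

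*Combined protocol and SAP*

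**What the plan says.** Section 8.2 describes a Simon two-stage design under which "accrual will be halted if we see greater than 5 UT's amongst the first 10 patients and greater than 11 amongst the first 30 patients". It introduces the limit more generally as a "decision threshold for the maximum number of UT's allowable in the study sample before we conclude that the regimen is unsafe". It also describes a single interim look, after stage 1, at which stopping is considered.

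Section 8.5 schedules three analyses. The interim is at the 10th patient's week 31. For the second, "the final analysis for the primary objective will take place after the last patient has reached the 31 week assessment time point". The third, for efficacy and exploratory objectives, is at three years. Items 2 and 3 are conditional only on the interim not having closed the trial.

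Section 9.0 carries over the first limit alone: "accrual will be halted if we see greater than 5 UT's amongst the first 10 patients recruited". It adds that the trial operations executive and the TMC "will review safety issues related to the trial through regular teleconferences held throughout the trial". Under 11.1 the TMC may continue, modify or stop the study "based on reports provided by the BaCT or other information". Under 7.2.5.1, "SAE reports and any other relevant safety information are to be forwarded within 24 hours", and 7.2.9 makes the sponsor responsible for "Ensuring that the coordinating principal investigator (CPI) or delegate is notified of each SAE".

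**The concern.** Thirty patients is the whole sample. A count read when the last of them reaches week 31 cannot halt accrual, however fast or slow enrolment is. The second half of the 8.2 sentence therefore has no scheduled moment at which it could be carried out.

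UT is the primary endpoint, and 8.2 adopts staging to reduce risk to patients. Once a 12th UT is confirmed, the final conclusion can only be that the regimen is unsafe. Nothing in the schedule would bring that fact to the TMC while further patients are being enrolled.

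The existing safety channels are real, but none is described as a tally of UTs against the limit. Serious-event reporting in particular does not track the endpoint. A UT under 3.1 also includes non-serious grade 3 or 4 events, two or more withheld cisplatin doses, less than 66% of the cisplatin dose delivered, radiotherapy beyond 7 weeks, and a pembrolizumab delay of more than 6 weeks.

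**Working it through.** **Inputs.** From 8.2: limits of at least 6 of 10 and at least 12 of 30; true rates of 0.3 (safe) and 0.5 (unsafe). From 8.3: 30 patients in two years, with accrual not suspended for the interim. From 8.5: readings at the 10th and the last patient's week 31. Assumed, because the documents do not give it: even accrual, and the time at which a UT becomes known.

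**Step 1: the plan's own figures.** With X1 ~ Bin(10, p) and X2 ~ Bin(20, p),

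P(unsafe) = P(X1 ≥ 6) + Σ(x = 0 to 5) P(X1 = x) · P(X2 ≥ 12 − x).

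- p = 0.3: 0.047 + 0.130 = 0.177 (stated 17%).
- p = 0.5: 0.377 + 0.528 = 0.905 (stated 90%).

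The stated figures reproduce to within a point. At p = 0.5, 52.8% of trials pass stage 1 and then end unsafe, so stage 2 produces most of the unsafe verdicts.

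**Step 2: timing.** One patient registers every 104/30 = 3.47 weeks. If the first registers at week 0, the 10th registers at 9 × 3.47 = 31.2 and reaches week 31 at about week 62, with 18 enrolled. If the first registers one interval later, the look is at about week 66, with about 19 enrolled. Enrolment closes at about week 104 and the final reading is at about week 135.

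**Step 3: error rates under a running count.** Halting at the 12th UT can occur only in a trial that already has more than 11. Every halted trial would have been concluded unsafe, so 17.7% and 90.5% stand.

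**Step 4: ceiling on the gain.** At p = 0.5, among trials that pass stage 1 and end unsafe, the 12th UT falls on average at patient 24.6. If UTs were known instantly, at most 30 − 24.6 = 5.4 patients would be spared in such a trial, or 0.528 × 5.4 ≈ 2.9 per trial overall.

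**Step 5: gain with a realistic lag.** Simulation with even accrual over 104 weeks. The halt is at the later of the 12th known UT and the 10th patient's week 31. Each cell gives the share of all trials halted early, then patients spared per trial.

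| UT known at | p = 0.3 | p = 0.4 | p = 0.5 | p = 0.6 |
|---|---|---|---|---|
| week 7 | 5.8%; 0.17 | 26%; 0.9 | 42%; 1.9 | 34%; 2.0 |
| week 13 | 4.1%; 0.11 | 20%; 0.65 | 37%; 1.5 | 32%; 1.6 |
| week 19 | 1.9%; 0.04 | 11%; 0.3 | 26%; 0.8 | 27%; 1.0 |
| week 31 | 0.3%; 0.005 | 3%; 0.05 | 10%; 0.2 | 15%; 0.3 |
| evenly over weeks 0–31 | 3.1%; 0.08 | 16%; 0.5 | 32%; 1.15 | 30%; 1.35 |

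The week-31 row has an exact check. About 21 patients have reached week 31 when the 30th enrols, and P(pass stage 1 and at least 12 UTs in the first 21) is 9.5% at 0.5.

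**Step 6: sensitivity at p = 0.5.** Patients spared per trial, across the same five timings, run from 0.01 to 1.9 with 78-week accrual and from 0.3 to 2.4 with 130-week accrual. Adding four weeks for reporting on the planned accrual gives 0.04 to 1.5.

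**Step 7: precision when the rule fires, p = 0.5.** Mean enrolment is 25.5 to 28.0. The mean Clopper-Pearson 95% width is 0.38 to 0.40, against 0.37 for the same trials at 30.

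**The case against.** The best answer is that the plan's intention is clear and the schedule is right for it. Section 8.2 names one stopping look, 8.5 treats only the interim as able to close the trial early, 9.0 attaches the halt only to the 10-patient count, and a Simon second boundary is ordinarily a final decision rule. On that view the only fault is one verb covering two thresholds, and a running stop is a feature the sponsor did not plan. Much of this stands: 8.5 is not in error, and no conclusion drawn from 30 patients would change.

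The gain also rests on assumed UT timing, and the TMC's meeting frequency is not stated, so the lower end of the range may be nearer the truth. On the other side, cisplatin failures are known by about week 6 and radiotherapy overrun just after week 7, so short lags are plausible for those components.

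A reader might infer more than this: that patients 11 to 30 are enrolled without safety oversight, or that the 17% and 90% are wrong. The documents support neither. Teleconferences run throughout, serious events are reported within 24 hours, and the TMC can modify or suspend the trial. The documents do not say what BaCT's reports contain; they schedule no UT count but do not exclude one. Both operating characteristics reproduce.

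**Conclusion.** The point holds as a minor one. The second halt described in 8.2 cannot operate on the 8.5 schedule; as planned, more than 11 of 30 is a final verdict only. Neither the design's error rates nor its final conclusion is affected.

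What is available is a small protection at little cost. It is worth about 0.2 to 1.9 fewer patients exposed per trial at a true rate of 0.5 on the planned accrual, and 0.01 to 2.4 if accrual takes 78 to 130 weeks. These figures assume even accrual and the UT timings shown, and they shrink with reporting delay. At the safe rate of 0.3 an early halt would occur in about 0.3% to 6% of trials on the planned accrual, all of which would be concluded unsafe in any case.

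**What to change.** In 8.2 and 9.0, state that after stage 1 BaCT reports the running number of confirmed UTs to the regular TMC teleconferences, and that accrual halts when the 12th is confirmed because the unsafe conclusion is then fixed. The count covers all registered patients except those replaced before treatment under 5.1.4. A UT counts once confirmed; week 31 is needed only to declare a patient free of one.

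For a trial halted this way, also state that:

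- all registered patients are followed to week 31;
- items 2 and 3 of 8.5 cover closure by this rule;
- complete response is reported descriptively, without the 18-of-30 rule;
- the UT interval method is named, for example Clopper-Pearson on all registered patients.

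On the last item, simulation of Clopper-Pearson used throughout gave at least 95% coverage. Using it only in halted trials and the two-stage methods of 8.3 otherwise has not been shown to keep that coverage.

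The cost is short edits and a tally sent through an existing route, with no new committee or data. When the rule fires at a rate of 0.5, the trial has about 25 to 28 patients, a slightly wider UT interval, fewer biomarker samples than the 30 planned in 8.4, and no complete-response decision. On the planned accrual that happens in about 0.3–6% of trials at 0.3, 3–26% at 0.4 and 10–42% at 0.5.

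If the sponsor wants only a final rule, 8.2 can confine the halt to the 10-patient look and say that more than 11 of 30 means the regimen is concluded unsafe. That is an editorial correction and adds no protection.

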9.0 SAFETY PARAMETERS/REVIEW AND MODIFICATIONS TO TRIAL

Given the experimental nature of the addition of pembrolizumab to concurrent chemoradiation, the following safety measures will exist

- 1) The trial operations executive (TOE) and the trial management committee (TMC) will review safety issues related to the trial through regular teleconferences held throughout the trial.
- 2) An additional safety review by the TMC will take place 12 weeks after completion of treatment for the 10th patient whereby accrual will be halted if we see greater than 5 UT's amongst the first 10 patients recruited using the Simon's two stage design described above in 8.2. Accrual can continue until the results of the interim analysis are available to the TMC.
- 3) Modifications to trial
 - a. Based on safety discussion the TMC may recommend to either
 - i. Omit concurrent pembrolizumab with chemoradiotherapy, and give pembrolizumab 200mg IV q3 weekly at week 7, 10, 13, 16 and 19 alone
 - ii. Modify the chemotherapy arm to allow either carboplatin, or 5FU/MMC [8]
 - iii. Suspend the study

iv. Any other modification suggested to reduce toxicity made by the TMC

The enrolment to the trial will be monitored by the TMC and if enrolment is reduced due to concerns regarding design of the trial, the TMC will suggest modifications that may include modification of the chemotherapy arm to allow concurrent carboplatin or 5FU/MMC.

10.0 LABELING, PACKAGING, STORAGE AND RETURN OF CLINICAL SUPPLIES

10.1 Investigational Product

The investigator shall take responsibility for and shall take all steps to maintain appropriate records and ensure appropriate supply, storage, handling, distribution and usage of investigational product in accordance with the protocol and any applicable laws and regulations. Detailed description is in the Pharmacy Manual.

Clinical Supplies will be provided by Merck and distributed by the central pharmacy are summarized in Table 11.

Table 11 Product Descriptions

Product Name & Potency	Dosage Form
Pembrolizumab 100 mg/ 4mL	Solution for Injection

10.2 Packaging and Labeling Information

Clinical supplies will be affixed with a clinical label in accordance with regulatory requirements.

10.3 Clinical Supplies Disclosure

This trial is open-label; therefore, the participant, the trial site personnel, the Sponsor and/or designee are not blinded to treatment. Drug identity (name, strength) is included in the label text; random code/disclosure envelopes or lists are not provided.

10.4 Storage and Handling Requirements

Clinical supplies must be stored in a secure, limited-access location under the storage conditions specified on the label.

Receipt and dispensing of trial medication must be recorded by an authorized person at the trial site.

Clinical supplies may not be used for any purpose other than that stated in the protocol.

